# Study Protocol

## Study Objectives

Our first aim is to integrate three distinct 'nudge' alerts into the UCLA Health EHR. Each nudge will test a different behavioural economics framing strategy. Our second aim is to conduct a four-arm randomised pragmatic trial to compare the effectiveness of the nudges to each other and to usual care. We hypothesise that exposure to the nudges will result in a reduction of pre-op tests ordered by physicians. We will randomise providers who conduct pre-op visits for patients with cataract surgery to one of four study arms: nudge 1, nudge 2, nudge 3 or no nudge (usual care) and measure the effect of the intervention on pre-op testing (see below).

## Trial design

This is a pragmatic, parallel group, open-label, randomised controlled superiority trial. Groups are allocated 1:1 to the intervention arms (nudges) and control arm (routine care). This trial will be conducted between June 2021 and June 2022 with a 12-month follow-up period. This trial has been registered with the United States Clinical Trials Registry. This protocol manuscript is compliant with the Standard Protocol Items: Recommendations for Interventional Trials statement. In this pragmatic trial of a quality improvement intervention, neither patients nor physicians provide consent to participate in the trial. This protocol was approved by the Institutional Review Board (IRB) of the University of California, Los Angeles (IRB#18-0 01 240).

## Methods

### Setting

This study will take place at UCLA Health, a large urban academic health system located in Los Angeles, California and surrounding communities. UCLA Health operates four hospitals on two campuses (Westwood and Santa Monica) and over 250 outpatient practices. Approximately, 2520 physicians and 4200 nurses provide care throughout the system.

### Participants

The participants in this study will be UCLA Health physicians who complete a pre-op visit for at least one patient undergoing cataract surgery at UCLA in the 12 months prior and 12 months after the study start date and all patients who are seen during such visits.

### Inclusion Criteria

All UCLA Health physicians perform a pre-op visit for a patient undergoing cataract surgery in the 12 months prior to the study start date as well as all physicians are anticipated to complete such a visit during the 12-month study period. In 2019, 322 physicians at 74 unique UCLA Health clinics performed such a visit. These physicians conducted a total of 1122 pre-op visits for 995 unique patients. To identify patients who presented for a pre-op visit within 30 days of cataract surgery, we used Surgical Consult Encounter Code 2100 in combination with one of four codes used to identify cataract surgery (3470, 2135, 4040, 4263).

### Exclusion Criteria

As this is a real-world pragmatic trial, all physicians who meet the criteria described above will be included in the study. Similarly, there are no exclusions for patients who present at a visit defined by the

criteria described above. Patients with cataract surgery who do not have a pre-op evaluation with a UCLA physician, but have cataract surgery at UCLA, will not be included in this study.

### Study Intervention

At UCLA Health, cataract surgery planning is initiated when a patient is evaluated by a UCLA ophthalmologist and deemed an appropriate candidate for the procedure. The patient is then asked to make an appointment for a pre-op visit with their primary care provider (PCP), cardiologist or another UCLA physician. The Centres for Medicare and Medicaid Services and the Joint Commission require that a pre-op visit be completed within 30 days of the surgery.

At this pre-op appointment, the provider completes a required history and physical, sometimes working off a checklist provided by the surgeon that may include a list of suggested tests such as EKG, cardiac stress test, Complete Blood Count (CBC), electrolytes and CXR. The ordering of these tests is left to the discretion of the physician completing the pre-op evaluation. The decision to order tests and procedures is influenced by the provider's previous experiences, preferences and interpretation of the guidelines.

The intervention will deploy one of the EHR nudge alerts (control, nudge 1, nudge 2 or nudge 3) such that each physician in the study will only get one of the nudges (or none of them) for the duration of the study. These alerts will be triggered when a physician begins to order a pre-op test for patients during their pre-op visit. The full list of pre-op tests, informed by Chen et al and Steinberg et al, was identified using Current Procedural Terminology codes. These tests fall into several categories including chemistry panel, complete blood count, coagulation panel, urinalysis, EKG, cardiac stress test, CXR and pulmonary function tests. The full list of pre-op tests can be found in the Appendix. Details of the nudge alert including opt-out features are described below.

To inform the design of the nudges for this study, we considered findings from Liao et al, which found that self-reported behaviour among physicians is most influenced by the patient and the potential for patient harm as compared with societal or institutional factors. We, therefore, tailored the three distinct nudges to highlight the following concepts: patient safety, financial costs to the patient and the risk of psychological harm to the patient. Each of the three nudge reference guidelines from the American Society of Anesthesiologists (ASA) and the American Academy of Ophthalmology (AAO) include links that physicians can access via the EHR. Given that one common reason for ordering cataract pre-op tests is the belief that they are required by the surgeon, we included specific language stating that UCLA ophthalmologists and anesthesiologists advise against pre-op testing. We also included text to reassure the provider that the pre-op team at UCLA will order any necessary labs on the day of surgery. In addition, each nudge includes an image relevant to the message of the nudge and the potential impact pre-op tests may have on patients.

### Three Intervention Arms

Nudge 1 will display as 'UCLA Ophthalmologists and Anesthesiologists ADVISE AGAINST routine pre-op tests, which do not increase the patient's safety and are considered inappropriate per current evidence-based recommendations (see UCLA Ophthalmology, UCLA Anesthesiology, ASA and AAO recommendations). The UCLA Pre-op Eval and Planning Center (PEPC) will order any necessary day of surgery labs'.

Nudge 2 will display as 'UCLA Ophthalmologists and Anesthesiologists ADVISE AGAINST routine pre-op tests, which can increase the patient's out-of-pocket costs and are considered inappropriate per current

evidence-based recommendations (see UCLA Ophthalmology, UCLA Anesthesiology, ASA and AAO recommendations). The UCLA PEPC will order any necessary day of surgery labs'.

Nudge 3 (figure 3) will display as 'UCLA Ophthalmologists and Anesthesiologists ADVISE AGAINST routine pre-operative tests, which can cause aggravation and psychological stress for the patient and are considered inappropriate per current evidence-based recommendations (see UCLA Ophthalmology, UCLA Anesthesiology, ASA, and AAO recommendations). The UCLA Pre-op Eval and Planning Center (PEPC) will order any necessary day of surgery labs'.

We designed these alerts to minimise the burden on physicians while also including a hard stop, so that if a physician chooses to order a pre-op test, they will need to type an explanation. This behavioural intervention is known as 'accountable justification', which has been shown effective in reducing low-value care. Specifically, as part of the alerts, physicians can remove the order with a single click on 'Accept'. If they choose not to remove the order, they can click 'Keep' and will be required to click on the 'Explain' button and provide free text stating why they continued with placing the order after exposure to the nudge

### Control Arm

Providers who are randomised to usual pre-op care will not receive an alert, or any special information about testing guidelines when they attempt to order a pre-op test. All other aspects of the clinical encounter and documentation will be the same for both the intervention and control arms.

### Data collection methods

All data will be collected from the UCLA Health EPIC EHR 'CareConnect' and from surveys administered to providers. This data will be stored securely and only accessible to research personnel trained in confidentiality and privacy procedures. An independent Data Safety Monitoring Board will provide ongoing oversight and data audits. To compare the cost of pre-op testing among study arms, we will use publicly available Medicare payment rates and UCLA Health commercial payment rates.

## Statistical Analysis Plan

### Randomisation Strategy

The study statistician will randomise eligible physicians to one of the two study arms. The randomisation will be stratified by the number of pre-op encounters conducted in the pre-intervention period (0, 1–2, 3–5,>6) to ensure appropriate control of physician's experience or preference to conducting pre-op testing.

### Primary and secondary outcome analysis

We will measure and compare rates of testing in the 12 months before and 12 months after initiation of the randomisation (primary outcome) to determine whether the EHR-based intervention is successful in changing physician behaviour. We will also compare each of the three intervention arms and the usual care arm and will perform exploratory comparisons between nudge 1, nudge 2 and nudge 3 (secondary outcome) to determine whether certain behavioural economic framing techniques are more effective than others at reducing pre-op testing.

Other secondary outcomes will include the percentage of patients who received specific categories of pre-op tests including labs, EKGs and CXRs, same-day surgery cancellations and physician-level

experience measured by the surveys. We will also estimate cost savings associated with the intervention (described below). Evaluation of the primary and secondary outcomes will be performed using generalised linear mixed-effects models at the patient level. We will investigate the impact of all nudges versus control, which will require a threefold correction. As a secondary analysis, we will conduct pairwise comparisons of the nudges. Models will include fixed nudge 1, nudge 2 and Nudge 3 effects, a fixed study period effect (postnudge intervention vs prenudge intervention), second-order interactions between these effects, a fixed stratum effect (hospitalist vs PCP) and random physician effects. Physician effects will account for clustering of patients by physician. Comparisons between changes in utilisation rates across study arms will be estimated and tested using model contrasts. All pairwise comparisons of changes between study arms will be performed to identify the most effective nudge, and Bonferroni corrections will be applied to control the familywise type I error rate at 5%. Intervention effects will be summarised using ORs, 95% CIs and p values (with multiple comparison corrections). Differences between strata will be similarly summarised.

These models will also be adjusted for patient-level covariates (age, race, ethnicity and Elixhauser comorbidities). Because serious complication rates are so low from cataract surgery (<0.1%), we will not have adequate power to determine whether the intervention is associated with a change in complication rates, but we will extract from the EHR all cardiovascular events occurring within 30 days of surgery and compare these in an exploratory fashion among the intervention and control groups. Analyses will be performed using SAS V.9.4 (SAS Institute, Cary, North Carolina).

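### The model's stratum term (hospitalist vs PCP) is not the factor used to stratify randomisation (visit volume), and some eligible physicians have no level in it

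*Combined protocol and SAP*

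**What the plan says.** - **SAP, Randomisation Strategy.** Randomisation is "stratified by the number of pre-op encounters conducted in the pre-intervention period", in four groups: 0, 1–2, 3–5 and >6. The stated purpose is to control for the physician's experience with, or preference for, pre-op testing. No other factor is named.
- **SAP, Primary and secondary outcome analysis.** The fixed effects are the three nudges, study period, their interactions and a stratum term; the full stratum and random part reads "a fixed stratum effect (hospitalist vs PCP) and random physician effects". The models are further "adjusted for patient-level covariates (age, race, ethnicity and Elixhauser comorbidities"). The tests are on changes: "Comparisons between changes in utilisation rates across study arms will be estimated and tested using model contrasts". The section also promises a summary of differences between strata.
- **Protocol, Study Intervention.** The patient books the pre-op visit "with their primary care provider (PCP), cardiologist or another UCLA physician".
- **Protocol, Exclusion Criteria.** No specialty is excluded: "all physicians who meet the criteria described above will be included in the study".
- **Protocol, Participants and Inclusion Criteria.** Participants asks for a qualifying visit "in the 12 months prior and 12 months after the study start date". Inclusion Criteria also covers physicians expected to see such a patient later: "all physicians are anticipated to complete such a visit during the 12-month study period".

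**The concern.** The word stratum means two different things in consecutive SAP sections. Two statisticians following the text could fit different models, one with volume bins and one with physician type.

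Applied literally, the written term has no value for a cardiologist or other specialist. Standard software drops records with a missing class variable, so those physicians' patients would leave the primary analysis, contrary to the protocol's inclusion of every qualifying physician. The alternative is to assign them to a level by a rule made after the data are seen. Because differences between strata are to be reported, the ambiguity also reaches a stated result.

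**Working it through.** **1. Text comparison.** The documents give no sample size, target power or intraclass correlation, so there is no design figure to reproduce.

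| | Randomisation | Analysis model |
|---|---|---|
| Factor | Pre-period encounters | Physician type |
| Levels | 0, 1–2, 3–5, >6 | Hospitalist, PCP |
| Volume term | Yes | None listed |
| Cardiologist or other physician | Falls in a volume bin | No level |

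Hospitalist appears nowhere else in the documents. Of the three kinds of physician named under Study Intervention (PCP, cardiologist, other), only PCP has a level in the model. The added adjusters are all patient-level, so none of them brings volume back in.

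**2. Inputs for the size of the effect.**
- From the documents: 322 physicians and 1122 visits in 2019, so 1122/322 = 3.48 visits per physician; a 65% baseline; a 30% effect. The Power section's (90 − 31)/2 = 29.5 supports reading that effect as percentage points, so 65% falls to 35%.
- Multiplicity: the SAP's threefold correction gives 0.05/3 = 0.0167, taken as two-sided.
- Assumed: geometric pre-period visits with mean 3.48; Poisson post-period visits around each physician's own pre-period count; arms balanced within bins; exactly 6 encounters placed in the top bin; random-intercept variance 0.25, 1 or 4 on the logit scale; bins explaining 5% or 20% of that variance; logit weights at 65% before and 50% after; and 0, 80 or 160 physicians with 0 encounters, averaging 1.74 or 3.48 post-period visits.

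The method is a weighted least-squares approximation to the logistic mixed model.

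**3. Leaving out the volume bins.** Standard error (SE) of a nudge-by-period contrast:

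| Scenario | Rise in SE without bins | Largest case (without vs with) |
|---|---|---|
| No 0-encounter physicians | 0.02% to 0.18% | 0.2500 vs 0.2496 |
| 80 or 160 added, mean 1.74 visits | 0.03% to 0.40% | 0.2423 vs 0.2413 |
| 80 or 160 added, mean 3.48 visits | up to 0.57% | 0.2390 vs 0.2376 |

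Percentages come from unrounded values. When the 0 bin alone differs by 0.5 or 1.0 log odds (1.74 visits), the mean between-arm shift is at most 0.002 log odds, with an SD per randomisation of at most 0.021, against an SE of about 0.25.

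A separate linear simulation under the null (intraclass correlation 0.2, 400 replicates) agrees. Type I error without vs with the volume term was 0.035 vs 0.035, 0.045 vs 0.048 and 0.060 vs 0.062 for volume effects of 0, 0.2 and 0.4 SD per stratum, with Monte Carlo error of about ±0.02.

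**4. Dropping physicians with no level** (random loss from the 322).
- 5% dropped: SE +2.7%. 10%: +5.7%. 20%: +12.6% (for example 0.2513 to 0.2830, and 0.2830/0.2513 = 1.126).
- Log odds ratio for 65% to 35%: ln(0.65/0.35) − ln(0.35/0.65) = 1.238.
- Power = Φ(1.238/SE − 2.394), where 2.394 is the normal quantile for two-sided 0.0167.
- Full sample: Φ(1.238/0.2513 − 2.394) = Φ(2.53) = 0.994. After a 20% loss: Φ(1.238/0.2830 − 2.394) = Φ(1.98) = 0.976.
- Across the three variances, power is 0.993–0.995 before and 0.973–0.979 after a 20% loss.

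**The case against.** The strongest reply is that the volume term hardly matters. The tests compare changes between arms, physicians carry a random effect, and stratified randomisation already balances volume. A stable difference between bins therefore largely cancels. That stands, and step 3 confirms it.

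Second, the only sizeable figures come from an assumed loss. No section gives the share of physicians who are neither type or says they would be dropped, and the protocol's inclusion of all qualifying physicians points against dropping them. The 12.6% is also close to what any 20% loss costs (1/√0.8 = 1.118). This stands too: the range illustrates the cost of losing records and does not estimate what would happen.

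Third, hospitalist vs PCP may be a deliberate physician-type covariate, since a model may contain factors not used in randomisation. That is possible. But the plan calls it the stratum effect straight after describing a different stratification, and it would still need a level for the remaining physicians. Random physician effects do not help here, because they handle clustering and do not give a cardiologist a level.

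**Conclusion.** The concern holds, as a minor point. That the two strata differ, that no volume term is listed, and that the coding is incomplete can all be read from the text with high confidence. The primary test is not invalidated: omitting the bins costs at most 0.57% in SE under the assumed inputs, and the between-arm shift is negligible. The practical risk is that records with no level are dropped or coded ad hoc. Even with 20% of physicians lost, power for 65% to 35% stays at or above 97%, provided the 30% means percentage points. Everything beyond the 322 physicians, 1122 visits, 65% baseline and 30% effect is assumed.

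A within-arm before–after change could move more if 0-encounter physicians are enrolled and test differently. Their number and their difference are unknown, and the between-arm comparison does not rest on that change.

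**What to change.** 1. Check both SAP sections against the randomisation actually performed, and make that factor the fixed stratum effect. If Randomisation Strategy is right, this means the visit-volume bins, with a bin assigned to exactly 6 encounters, which the listed groups leave out.
2. If physician type is wanted, keep it as a separate covariate with a level for every eligible type (PCP, hospitalist, cardiologist, other), so that no eligible physician's patients are lost.
3. State which factor the summary of differences between strata covers.
4. State whether physicians with 0 pre-period encounters are enrolled. Participants can be read as excluding them, while Inclusion Criteria and the 0 group in Randomisation Strategy point the other way.

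**Cost.** SAP wording and a check of the randomisation list. Four bins use 3 degrees of freedom. If they replace the two-level term, the net addition is 3 − 1 = 2, or 2 − 1 = 1 if there is no 0 bin. If type is kept and expanded from two to four levels, the net addition with four bins is 3 + 2 = 5. The bins need no new data; physician type must be recorded for every physician if it is kept.

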### Power

Preliminary analyses of UCLA Health data show that the baseline rate of testing is 65%. In a prior quality improvement study conducted at a different health system, we reduced pre-op lab testing by 59% (a reduction from 90% to 31%). We conservatively estimate an effect half as large (30%) in each intervention arm.

To calculate savings from reduced use of medical services, we will multiply the estimates of utilisation (ie, quantity) for each of the pre-op services measured by the relevant payment rates for the services based on the coverage type for the patient (ie, Medicare and average commercial payment rates per service). We will then compare differences in spending overall and by specific services (ie, lab testing, EKGs) between the control arm and each of the intervention arms and a pooled estimate of the three-nudge intervention arms. We will disaggregate the savings to measure the amount and proportion accrued by the health system/payer versus the patient. An extension of this analysis will estimate how reducing the utilisation of pre-op testing affect different parties; we will disaggregate the savings estimates by type of payer contract (ie, capitated vs fee-for-service(FFS)) to derive estimates of savings to the health systems versus the payer. Under capitated payments, the savings accrue to the health system, while under FFS payments, the savings accrue to the payer and represent revenue losses for the health system.

We will extrapolate observed saving estimates to compute savings the Medicare FFS programme might expect to accrue if similar reductions in the utilisation of pre-op services for cataract surgery were observed in the Medicare population. To generate these savings estimates, we will compute the number of Medicare patients undergoing cataract surgery in a single year and the fraction of patients who have these pre-op tests. We will then take our estimates of reduction in utilisation and apply these estimates to the current use of pre-op testing utilisation in the Medicare FFS programme to determine the number

of services that would be reduced. We would then apply FFS payment rates to the number of services that would be reduced to estimate savings to Medicare. Finally, we will develop estimates of longer term savings in a year–year time range, applying a discount rate to costs, assuming that the observed reduced amount of services used remained similar after the 1-year study period ended.

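### The primary model names only random physician effects for a before/after contrast; read as an intercept, it omits physician-specific change, and the 5% familywise error is not protected

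*Combined protocol and SAP*

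**What the plan says.** Under Randomisation Strategy the unit of randomisation is the physician: "The randomisation will be stratified by the number of pre-op encounters conducted in the pre-intervention period", in bands of 0, 1–2, 3–5 and >6 visits.

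Under Primary and secondary outcome analysis, the model is a patient-level generalised linear mixed model. It has fixed nudge effects, a fixed period effect and their interactions, plus "a fixed stratum effect (hospitalist vs PCP) and random physician effects". The tests are on change: "Comparisons between changes in utilisation rates across study arms will be estimated and tested using model contrasts". On error control, "Bonferroni corrections will be applied to control the familywise type I error rate at 5" per cent, with a threefold correction for the nudges against control.

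The stated job of the random term is: "Physician effects will account for clustering of patients by physician". Neither the protocol nor the SAP names a physician-by-period effect, a random period slope or a robust variance.

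**The concern.** When the tested quantity is a before/after change, a stable physician effect largely cancels. What remains at the level of the randomised unit is how much each physician changes. All of a physician's visits in one year share that change, so they do not carry independent information about it. A model with only an intercept treats the change as independent patient noise and understates the standard error of each nudge-by-period contrast.

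Bonferroni corrects for the number of tests, not for a standard error that is too small. The p values and 95% intervals for every nudge would then be too optimistic.

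Such change is plausible. The Study Intervention section says ordering depends on the provider's "previous experiences, preferences and interpretation of the guidelines", and these can move from one year to the next. Physicians may also differ in how they respond to the same hard-stop alert, which creates physician-specific change even without drift. This matters most for the nudge-versus-nudge comparisons, where the arms may truly be equal.

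**Working it through.** **1. Inputs from the documents.** "In 2019, 322 physicians at 74 unique UCLA Health clinics performed such a visit" (Inclusion Criteria). These physicians made 1122 visits, so 1122/322 = 3.48 visits per physician-year and 322/4 = 80.5 physicians per arm. Baseline testing is 65% (Power). The familywise alpha is 5%.

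**2. The plan's own figure.** Three tests at 0.05/3 = 0.0167 sum to 0.05, so the 5% follows if each test has its nominal size. If the family is all six pairwise tests, each is run at 0.05/6 = 0.0083.

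**3. Why an intercept is not enough.** Let a physician's tendency (logit scale) be a stable part b plus a period-specific part c, with variances σ_b² and σ_c². The between-year correlation is ρ = σ_b²/(σ_b² + σ_c²). In a linear analogue, with n₀ and n₁ visits before and after and patient variance σ_e², the variance of one physician's change is

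σ_e²(1/n₀ + 1/n₁) + 2σ_c².

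The stable part cancels. The term 2σ_c² does not shrink with more visits per physician, and the intercept model leaves it out unless ρ = 1.

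**4. Assumptions.** The documents give no ICC, no ρ and no visit distribution. Assumed here: latent ICC 0.2 to 0.4; ρ from 1.0 to 0.6; visits either even (Poisson, mean 3.48) or skewed (gamma-Poisson, shape 0.8, median 2, 90th percentile 8, 13% of physicians with no pre-period visit). An unconditional gamma-Poisson with shape 0.8 and mean 3.48 would give (0.8/4.28)^0.8 = 26% with none. A figure of 13% matches a version that drops physicians with no visit in either year and uses an underlying mean of about 2.86. Logistic mixed models were fitted by maximum likelihood with numerical quadrature, without patient covariates or the hospitalist/PCP term.

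**5. Familywise error under the null, intercept only, three tests at 0.05/3** (1500 runs per setting; Monte Carlo SE 0.5 to 1.0 points):

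| ρ | Even visits, ICC 0.2 / 0.3 / 0.4 | Skewed visits, ICC 0.2 / 0.3 / 0.4 |
|---|---|---|
| 1.0 | 4.7 / 3.3 / 4.0% | 4.1 / 4.7 / 5.2% |
| 0.9 | 5.6 / 5.6 / 6.8% | 5.9 / 7.4 / 9.1% |
| 0.8 | 5.9 / 7.3 / 9.3% | 7.1 / 9.5 / 11.9% |
| 0.6 | 7.5 / 9.7 / 12.3% | 11.7 / 13.7 / 18.2% |

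For all six pairwise tests at 0.05/6 the ranges are 3.3-4.9%, 5.3-9.7%, 5.9-13.3% and 8.1-22.4% at ρ = 1.0, 0.9, 0.8 and 0.6.

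**6. Hand check** (ICC 0.3, skewed, ρ = 0.8). The median model SE is 0.291 and the true SD of the estimate is 0.333, a ratio of 0.874. The critical value for 0.05/3 is 2.394, so the effective cut-off is 2.394 × 0.874 = 2.092, with a two-sided tail of 0.0364 instead of 0.0167. Three such tests have a familywise error of at most 3 × 0.0364 = 10.9%. The simulated 9.5% lies below this bound, as expected for tests that share a control arm.

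**7. A second, separately coded simulation** used intercept SD 1.0 and physician-by-period SD 0, 0.5, 0.75 and 1.0 (ρ = 1.0, 0.80, 0.64, 0.50). The intercept-only familywise error was 4.6, 7.4, 9.3 and 11.9% with even visits and 4.1, 11.9, 18.0 and 27.3% with skewed visits.

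**8. With a physician-by-period effect added.** For ICC 0.3 and skewed visits the error is 4.5, 5.5 and 4.7% at ρ = 1.0, 0.8 and 0.6. At ρ = 0.8 the model SE is 0.335 against a true SD of 0.337. In the second simulation the error is 3.8 to 5.9% for three tests over all settings.

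**9. Differing response without drift.** With three equally effective nudges and a physician response SD of 0, 0.5 and 1.0 (logit, assumed), false nudge-versus-nudge findings under the intercept model were 4.1, 7.3 and 16.2% at 0.05/3 per test. At 0.05/6 they were 2.2, 3.5 and 9.8%, where three tests should give at most 3 × 0.05/6 = 2.5%.

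**The case against.** The SAP never says intercept. The wording is plural and unspecified, and if a physician-by-period effect was meant, the problem disappears. This stands: the finding is conditional on a reading. That reading is still the natural one, since the only stated role is clustering by physician and no term varying by period is named.

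No passage shows that physicians drift; the Study Intervention text makes it plausible and no more. With even visits and ICC 0.2, errors of 5.6% and 5.9% cannot be told from 5% given the simulation error. The largest figures come from the end of an assumed grid and from an assumed visit distribution, and the two simulations differ under skew (9.5% against 11.9% at ρ = 0.8). These points limit the size, not the direction. The randomisation bands, from 0 to above 6, do allow for uneven volume.

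The simulations also leave out patient covariates, the 74 clinics and repeat visits (1122 visits, 995 patients). The corrected standard error is therefore right for the simulated model and not guaranteed for the real data.

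Finally, if the planned effect occurs ("We conservatively estimate an effect half as large (30%) in each intervention arm"), nudge versus control will be significant either way. That is fair for those three tests. It does not help the nudge-versus-nudge comparisons or the width of the reported intervals.

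**Conclusion.** The concern holds. With the physician effect read as an intercept, the stated 5% familywise error is assured only if each physician's tendency is the same in both years apart from the fixed effects. Otherwise the tests are too liberal. The direction follows from the design. The size does not follow from the documents: over the assumed ICC of 0.2 to 0.4 and either visit pattern, the three-test error is 5.6-9.1% at a between-year correlation of 0.9, 5.9-11.9% at 0.8 and 7.5-18.2% at 0.6. It is close to nominal when visits are even and the ICC is low, and worst when a few physicians make many of the visits. The change should be made before analysis; confidence is medium because the model wording is open and the variance components are unknown.

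**What to change.** **(1) State the random-effects structure and add a physician-by-period effect**, for example in PROC GLIMMIX:

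`random intercept / subject=physician;`
`random intercept / subject=period(physician);`

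Name the estimation method as well; the figures above are for quadrature maximum likelihood. Pre-specify a fallback if the added variance cannot be estimated: the intercept model with empirical standard errors clustered by physician. In the runs above, that variance was estimated near zero in 3% of trials at ρ = 0.8 and in 63% at ρ = 1.0, where its true value is zero. The fallback used alone had a familywise error of 3.9-6.5% over the 24 settings, so it is slightly liberal. The combined rule of fitting first and then switching was not simulated.

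**(2) Optional, and only together with (1):** drop the three nudge main effects so that all randomised arms share one pre-period mean, keeping the nudge-by-period terms as the treatment effects. This gains precision but does not cure the error: without (1) the familywise error was 4.9, 8.6 and 11.3% at ρ = 1.0, 0.8 and 0.6, and with (1) it was 4.4, 4.1 and 4.3%. It relies on analysing all randomised physicians.

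**Cost.** SAP wording and one or two lines of code; no new data. At ICC 0.3, ρ = 0.8 and skewed visits, (1) raises the standard error from 0.291 to 0.335 (0.335/0.291 = 1.15). Power per contrast for a fall from 65% to 35% goes from 99.9% to 99.2%. Adding (2) brings the standard error to 0.280 and simulated power to 100%.
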